Study Subjects and Eligibility Criteria Patients with a diagnosis of symptomatic cholelithiasis or biliary colic who were >18 years of age and enrolled in the Primary Care Service Line (PCSL) Registry in Clarity or evaluated and discharged from the Emergency Department (PAH, PPMC and HUP) between Jan. 1 2020 and Sept. 30, 2022 will be eligible for inclusion (data will be obtained for January 1 2020 to Dec. 31, 2022). The Primary Care Service Line (PCSL) covers more than 500,000 patients across the Penn Medicine catchment area including 12 contiguous urban, suburban, and rural counties in the tri-state area of PA, NJ, and DE (See Figure). The population is approximately 37.6% Black and 7.5% underinsured. Symptomatic cholelithiasis and biliary colic will be identified using International Classification of Diseases, Tenth Revision, Clinical Modification codes (ICD-10-CM). A 6-month “look-back” will be performed to confirm the first instance of disease. Patients with the following criteria will be excluded from study: 1) history of prior cholecystectomy 2) prisoners, or 3) contraindication to cholecystectomy including GB cancer, advanced cirrhosis and untreated coagulopathy.

Data Sources and Elements Clinical data will be abstracted from Clarity and financial data from the Horizon Performance Manager (HPM) dataset. This will allow real-world calculations of the value of care at Penn Medicine.

Definition of Social Vulnerability: Race will be the primary independent variable, given the established association between race and surgical disparities in the literature and preliminary data from Penn Chart. Ethnicity (Hispanic/non-Hispanic), primary language (English/non-English), insurance (Medicaid, Medicare, private, other) and low-income neighborhood (home zip code) will be identified in Clarity.

Covariates: Age, sex, comorbidities (defined by Elixhauser et al [28] using the index PCP visit and a 6-month look-back period), history of cholecystectomy, GB cancer, cirrhosis, coagulopathy and diagnostic imaging (US and CT SCAN) information will be obtained from Clarity. ICD-10 diagnosis codes will be used for clinical diagnoses. Date diagnosis add to chart, date of confirmatory imaging, date of discussion of treatment, date of referral to a surgeon and prisoner status will be obtained via direct chart review of PCSL notes within the 3-months following the initial diagnosis of SGBD. Access point will be designated as PCSL or Emergency Dept..

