Clinical Outcomes: Surgical consultation will be obtained from Horizon Performance Manager (HPM) via CPT codes for consultation. [29] Operative treatment will be determined using CPT and ICD-10-PCS codes for cholecystectomy as listed in HPM (CPT 47562, CPT 47563, CPT 47600, CPT 47605, CPT 56340, CPT 56341, ICD10 0FB40ZX, ICD10 0FB40ZZ, ICD10 OFT40ZZ) and operative urgency (emergent/urgent vs elective) will be based on the admission source for the associated operative encounter. We hypothesize that Black patients are less likely to undergo cholecystectomy in the elective setting than White patients (H1.1), that time to

consultation will modify the effect of race on elective cholecystectomy (H1.2), and that underinsurance (e.g., Medicaid) will exacerbate the effect of race on outcomes.

Financial Outcomes: We will assign costs using data from HPM for billable encounters in the emergency department, inpatient setting and ambulatory procedure units with a primary diagnosis related to symptomatic cholelithiasis and biliary colic within 90-days of diagnosis. Permutations of cost will be assessed with nonparametric tests and regression. We hypothesize that costs will be higher for Black patients and impacted by other SV factors (H1:4). Stratified analysis will be performed by treatment group and point of access.

Analytic Strategy In order to adjust for potential confounders, multivariable regression (logistic and robust) will be used to explain the relationship between race and outcomes. Interaction terms will be used to examine effect modification of social vulnerability factors on the relationship between race and outcomes. The marginal effects of social vulnerability factors will be calculated. All analysis will be performed using STATA Version 17 (Stata Corporation, College Station, TX).

PRELIMINARY STUDY RESULTS and POWER CALCULATIONS

Our preliminary data from Penn Chart demonstrate racial disparities in access to care with a greater proportion of Black PCSL patients undergoing emergent cholecystectomy than White patients (see Equity section). We will be powered at 80% with an alpha of 0.05 to detect differences between Black and White patient outcomes as small as 5%. Note that preliminary data shows a difference of 24% in emergent chole.

[figure not shown]
Telemedicine Consultation as a Mechanism to Improve Surgical Health Equity in Benign Disease (AIM 2)

Design Pragmatic pilot trial.

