ensure capture of visits outside of Penn Medicine. Secondary outcomes will include time to consultation, proportion to undergo cholecystectomy, time to surgery, and emergent/urgent vs elective operation.

Data Analysis Descriptive statistics will be performed. Univariate comparisons to test hypotheses will be performed using the chi-square test or Fisher's exact test for categorical data and t-test or Wilcoxon rank-sum for continuous data. Statistical analysis will be performed using STATA Version 17 (Stata Corporation, College Station, TX). Stratified analyses will be performed by race, ethnicity, primary language, median neighborhood income, and insurance status as permitted by sample size.

PRELIMINARY STUDY RESULTS and POWER CALCULATIONS

In addition to providing preliminary evidence of the efficacy potential of telemedicine surgical consultations, the goal of the pilot study is to estimate recruitment and retention rates and population variance of social vulnerability factors. Because we want to be powered to detect small effect sizes, ($0.1 \leq d < 0.3$) where d is the standardized difference, we will target enrollment of 20 participants per group to achieve a power of 80%, $\alpha=0.05$. [32]

Limitations

- The study focuses on patients already connected to primary care providers. Many patients with SV may not reach that point in the health system. However, in clinical practice at Penn Medicine it is not uncommon for patients to have insurance that allows primary care at our community sites without providing benefits for surgical care for nonemergency conditions. This approach to patient care exposes patients treated in our community to the excessive clinical and financial risks associated with emergency surgery. Because we will conduct an explanatory analysis of factors associated with surgical consultation and treatment, we will identify barriers to surgical health equity (e.g., insurance coverage) within our system. This will allow us to develop strategies to achieve health equity at the system level.

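### Aim 1 finds consultation, cholecystectomy and urgency only in HPM, so care received outside Penn Medicine is scored as not done; the plan has no check for differential capture by race or insurance.

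*Combined protocol and SAP*

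**What the plan says.** **Aim 1, Clinical Outcomes.** On consultation: "Surgical consultation will be obtained from Horizon Performance Manager (HPM) via CPT codes for consultation". On surgery: "Operative treatment will be determined using CPT and ICD-10-PCS codes for cholecystectomy as listed in HPM". On urgency: "operative urgency (emergent/urgent vs elective) will be based on the admission source for the associated operative encounter".

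**Aim 1, Data Sources and Elements.** "Clinical data will be abstracted from Clarity and financial data from the Horizon Performance Manager (HPM) dataset". The stated purpose follows: "This will allow real-world calculations of the value of care at Penn Medicine". The text does not say outright that HPM holds only Penn encounters, but that is its natural reading.

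**Aim 1, Covariates.** A set of dates (diagnosis, imaging, treatment discussion, referral) and prisoner status "will be obtained via direct chart review of PCSL notes", limited to the three months after first diagnosis. Completed consultations or operations elsewhere are not on that list.

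**Aim 2, Outcomes.** Consultation is found by chart review that includes Care Everywhere, in order to "ensure capture of visits outside of Penn Medicine". No such step is stated for cholecystectomy in Aim 2.

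**Limitations.** The protocol notes that "it is not uncommon for patients to have insurance that allows primary care at our community sites without providing benefits for surgical care" when the condition is not an emergency. It presents this as a barrier that the analysis may identify, not as a problem of outcome capture.

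No section gives Aim 1 an outside-record step, a leakage or censoring rule, or a sensitivity analysis for care received elsewhere.

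**The concern.** Consultation is measured in two ways in one protocol, and the aim that tests the race hypotheses has the narrower method. As written, Aim 1 cannot tell a patient who was never treated from one who was treated at another institution.

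This matters most if the loss is uneven. The insurance pattern in the Limitations gives a plausible route: a patient without cover for non-emergency surgery might have an elective operation elsewhere, unseen by HPM, while an emergency operation at Penn is counted. If that happens, and is more common in Black patients, the recorded elective rate falls in that group for reasons of capture. That is the direction of H1.1. It could also distort the planned interaction in which underinsurance worsens the effect of race. Adjusting for insurance category may reduce the error but does not restore a misclassified outcome.

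**Working it through.** **Inputs.** Emergent operations among operated patients, from Penn Chart (Equity Plan and Impact): Black 76/117, White 125/303. PCSL underinsured 7.5% and Black 37.6% (Aim 1 eligibility section). Black patients with symptomatic gallbladder disease: 1,978, or 21% of about 9,400. The documents give no leakage rate and no insurance mix by race.

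**1. The plan's own figure.** 76/117 = 65.0% and 125/303 = 41.3%. The difference is 23.7 points (24 in the protocol), with chi-square p of about 0.00001 uncorrected and 0.00002 with continuity correction. The stated p < 0.001 reproduces.

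**2. Only Black elective operations missed.** Observed Black elective operations: 117 − 76 = 41. With m missed, the Black emergent share is 76/(117 + m), and the share of all Black elective operations that went unseen is m/(41 + m).

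| m | Black emergent share | Gap to 41.3% | Share of Black elective operations unseen |
|---|---|---|---|
| 20 | 76/137 = 55.5% | 14.2 points | 20/61 = 33% |
| 40 | 76/157 = 48.4% | 7.2 points | 40/81 = 49% |
| 67 | 76/184 = 41.3% | about 0 | 67/108 = 62% |

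The last column is the relevant denominator. Set against all 1,978 diagnosed Black patients, 67 is only 3.4%, which makes an extreme case look small.

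**3. Other leakage patterns.**
- *Same share of elective operations missed in both groups.* White elective observed: 303 − 125 = 178. Missing 87 is 87/265 = 33%, so the White share becomes 125/390 = 32.1%. Against 55.5% the gap is 23.4 points, almost unchanged.
- *Black emergency operations missed instead.* With 20 missed, (76 + 20)/(117 + 20) = 70.1%, and the gap widens to 28.8 points.
- *20 of each missed in Black patients.* 96/157 = 61.1%, a gap of 19.9 points.

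So the direction depends on what leaks and from whom.

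**4. A bound from the stated underinsurance.** Assume that the true emergent share is e = 41.3% in both races, that every underinsured patient has elective surgery elsewhere, and that every emergency is seen. With a fraction x of elective operations missed, the observed emergent share is e/(e + (1 − e)(1 − x)).
- All underinsured patients Black: x = 7.5/37.6 = 19.9% gives a false gap of 5.5 points. With 1,978/9,400 = 21.0% Black, x = 35.6% gives 10.9 points.
- Underinsurance twice as common in Black patients: 1.5 to 1.7 points.
- Equal by race: no gap.

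**5. Effect on a test of elective rates.** Assume 1,978 Black and 9,400 − 1,978 = 7,422 other patients, equal true elective rates, and leakage in Black patients only. These group sizes are an assumption; the Aim 1 cohort size is not stated. Chance of a false significant result (two-sided 0.05):

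| True elective rate | 10% of Black elective operations missed | 20% missed |
|---|---|---|
| 5% | 14% | 45% |
| 10% | 26% | 78% |
| 20% | 51% | 98.5% |

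In a cohort of this size, modest differential capture can reach significance even when the absolute gap is small (1 to 4 points at 20% missed).

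**The case against.** The Limitations do not say that patients without surgical cover are operated on elsewhere. The passage goes on to say that they are exposed to the risks of emergency surgery, which suggests that many stay untreated until they present acutely. HPM would then classify them correctly, and a low elective rate would be the real barrier that Aim 1 seeks. This stands, and it is why the mechanism can only be conditional.

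The race link is also an inference. PCSL spans 12 counties in three states, so leakage may follow geography as much as insurance, and emergency operations at other hospitals would be missed too.

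A reader might infer that outside surgery explains the preliminary 24-point difference. The documents do not support that. It would need 62% of Black elective operations unseen and no White ones, and the stated 7.5% underinsurance cannot produce it even on the most extreme allocation. Moreover, the preliminary figures come from Penn Chart, are not said to come from HPM, and describe emergent share among operated patients, whereas the Aim 1 primary outcome is cholecystectomy in the diagnosed cohort.

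Finally, insurance is a planned effect modifier, and parts of the protocol frame the work as care within the Penn system. That reduces the problem but supplies neither outside capture nor a statement that the outcomes are limited to Penn.

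**Conclusion.** The point holds as a gap in outcome capture: Aim 1 scores outside consultation and cholecystectomy as not done and plans nothing to measure or bound the effect. This rests on reading HPM as a Penn-only dataset.

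Bias in H1.1 or in the race-by-insurance interaction is possible, not shown. It requires that some patients have surgery elsewhere and that this differs by race; the documents are silent on both. Size and direction are therefore unknown, and the figures above are illustrations under stated assumptions. It would go too far to say that the planned data source creates the disparity, or that its error must run towards H1.1. It is a worthwhile, inexpensive improvement because it changes what Aim 1 may conclude.

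**What to change.** 1. Pre-specify a tipping-point analysis for differential outside capture by race and insurance category, varying missed elective and missed emergency operations in both race groups. It should state how much differential leakage would overturn each Aim 1 conclusion.
2. In a random sample stratified by race and insurance category, check Care Everywhere for outside consultation and cholecystectomy over the Aim 1 data window (1 January 2020 to 31 December 2022). Report capture rates by stratum and use them to set the range in item 1. The operation item needs its own definition, since Aim 2 states outside capture only for consultation.
3. Define and report the Aim 1 outcomes as consultation and cholecystectomy *at Penn Medicine*, and name possible leakage in the Limitations.

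An analysis restricted to patients whose insurance covers elective surgery at Penn should not be promised unless plan-level data are available. The planned variable (Medicaid, Medicare, private, other) does not identify them.

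**Cost.** Item 1 needs analyst time and item 3 only wording. Item 2 needs real abstraction time, because it uses a different source and a longer period than the planned three-month review of PCSL notes; sampling keeps it manageable. The stated conclusion also becomes narrower.

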Gallbladder (GB) disease is extremely common, affecting 10% to 20% of White adults in the United States with the prevalence rising as high as 70% in specific ethnic groups. [1] Up to 5% of patients with gallstone disease become symptomatic within 1-year. [2] The incidence is greatest among obese people placing patients from racial and ethnic minority groups and those from low-income backgrounds at the greatest risk of disease. [3] Elective cholecystectomy is recommended for patients with symptomatic cholelithiasis or biliary colic. [4] Laparoscopic cholecystectomy is a safe and effective treatment that can be performed in the outpatient setting with complication rates ranging from 0.5-6.0%. [5]

Delayed treatment for symptomatic cholelithiasis and biliary colic often results in acute cholecystitis and related diseases that necessitate emergency surgery. [6] For example, patients waiting 20 weeks or more for elective cholecystectomy were more likely to undergo admission for emergency cholecystectomy than those waiting shorter times. [7] Emergent cholecystectomy results in worse outcomes with almost two-fold higher rates of conversion from laparoscopic to open, increased hospital length of stay by an average of over 5 days, increased rates of morbidity (8.8 vs 3.7%) and mortality (2.6 vs 0.5%), and higher costs (mean charge difference over \$6,000) when compared to elective cholecystectomy. [8-10]

Black and Hispanic patients, non-English primary language speakers, and those living in areas of greater social vulnerability are at increased risk of emergent GB surgery when compared with White, English primary language speakers, and those from well-resourced communities. [11-14] Barriers to timely consultation and surgery among historically marginalized communities include patient- and system-level factors. For example, work conflicts, limited paid time off, long clinic wait times, and limited ability to contact the surgical clinic often preclude the ability of patients with social vulnerabilities to seek a consultation or receive elective, operative care.[15-18]

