Aim 1: Examine racial disparities in outcomes of PCSL patients with symptomatic GB disease with attention to conditional effects of social vulnerabilities. Hypothesis 1.1: Black patients are less likely to undergo cholecystectomy in the elective setting than White patients. Hypothesis 1.2: Time to consultation will modify the effect of race on elective cholecystectomy. Using PennMedicine data we will perform a retrospective cohort study of PCSL patients diagnosed with symptomatic GB disease between Jan. 1 2020 and Sept. 30, 2022. The primary independent variable will be race. Primary outcome will be cholecystectomy. Secondary outcomes will include time from referral to consultation and treatment, completion of consultation, urgency of operative treatment, and cost. Regression models with interaction terms will be used to evaluate effect modification of additional social vulnerability factors (e.g., ethnicity, primary language, insurance, income) on outcomes.

Aim 2: Comparative effectiveness study of telemedicine consultation for symptomatic GB disease in patients with social vulnerability (SV). Hypothesis 2.1: Recruitment will be feasible in the three-month pilot period. Hypothesis 2.2: Time to telemedicine consultation will be shorter than in-person consultation. We will perform a pilot study of telemedicine vs in-person surgical consultation for patients with SV with symptomatic GB disease seen in PCSL clinics between January and June 2023. Rates of surgical consultation will be compared between groups by consultation type. Secondary outcomes will be examined.

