Social vulnerability (SV) is a complex concept with many definitions that are situationally dependent. For this proposal, we define social vulnerability by race, ethnicity, primary language, insurance, and income, five components known to be associated with disparities in care for patients with SGBD. Preliminary data show that the majority of the Penn Medicine PCSL population with SGBD meet our criteria for SV (Black race, 21% (n=1978); Hispanic 6% (n=565); non-English primary language 4% (n=376); low-income neighborhood 91% (n=8573)). Further, in preliminary data, when examining differences across racial groups, for example, Black PCSL patients treated within the past 6 months at PennMedicine were more likely to undergo emergent (vs elective) cholecystectomy than White patients (Black: 65% (76/117); White: 41% (125/303); p<0.001). Emergent operations are associated with worse outcomes and greater costs.

Using data abstracted from PennChart, we will conduct an observational study of patients seen within the PCSL and the those discharged from the Emergency Department with symptomatic cholelithiasis and biliary colic between Jan. 1, 2020 and Sept. 30, 2022. These data will allow us to examine quality of care in two dimensions, safety and efficiency, for patients treated in the community setting. While we focus our analysis on race, we will study the conditional effects of other dimensions of SV on quality. **To date, the reasons for and impact of delays in treatment of symptomatic GB disease in Black patients and those with other SV within our PennMedicine community is unknown.** To test a solution to the problems of time off work and transportation, we will enroll patients with SV seen in the PCSL clinics in a pilot designed to test telemedicine as a mechanism to improve timely access to surgical care. Health equity will be measured by rates of surgical consultation among patients with SV and timeliness of surgical consultation and treatment.

RESEARCH PLAN AND METHODOLOGY

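### The ICD-10-PCS codes listed for cholecystectomy in Aim 1 appear to be open-approach only, so a laparoscopic operation recorded in HPM by PCS code alone would be missed

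*Combined protocol and SAP*

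**What the plan says.** The Aim 1 statement under Aims and Significance sets the endpoint: "Primary outcome will be cholecystectomy". Under Clinical Outcomes (Aim 1), "Operative treatment will be determined using CPT and ICD-10-PCS codes for cholecystectomy as listed in HPM". The list has six CPT codes, beginning "CPT 47562, CPT 47563, CPT 47600, CPT 47605", and ends "CPT 56340, CPT 56341, ICD10 0FB40ZX, ICD10 0FB40ZZ, ICD10 OFT40ZZ".

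The same paragraph derives urgency from the matched operation: "operative urgency (emergent/urgent vs elective) will be based on the admission source for the associated operative encounter". An operation that is not matched therefore has no urgency either.

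The plan does not define any code. It does not say whether one match of either type is enough, or which HPM encounters carry CPT codes. The chart review described under Covariates (Aim 1) covers diagnosis, imaging, treatment-discussion and referral dates and prisoner status. It does not confirm operations.

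The background section makes clear which operation is meant: "Laparoscopic cholecystectomy is a safe and effective treatment that can be performed in the outpatient setting". Future Directions contrasts elective same-day surgery with emergency inpatient care. The Equity section gives preliminary emergent shares: "Black: 65% (76/117); White: 41% (125/303); p<0.001".

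**The concern.** The plan is mainly about laparoscopic surgery, yet the PCS part of its case-finding list appears to contain only open-approach codes. Laparoscopic operations are then found only through CPT codes. Where HPM holds an inpatient operation by PCS code alone, the patient would be counted as not operated.

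Such a gap need not be neutral. The plan itself associates emergency surgery with inpatient care and reports a higher emergent share in Black patients. If PCS-only recording is concentrated in those stays, the list would create or enlarge a deficit in cholecystectomy among Black patients. Costs are assigned by diagnosis and then stratified by treatment group, so the cost of a missed operation would also fall in the wrong stratum.

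**Working it through.** **The codes.** Characters 1 to 7 of the three PCS codes:

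| Code | 1 | 2 | 3 | 4 | 5 | 6 | 7 |
|---|---|---|---|---|---|---|---|
| 0FB40ZX | 0 | F | B | 4 | **0** | Z | X |
| 0FB40ZZ | 0 | F | B | 4 | **0** | Z | Z |
| OFT40ZZ | O (letter) | F | T | 4 | **0** | Z | Z |

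That the fifth character is 0 throughout can be read off the page. Its meaning is taken from the public nomenclature and is an assumption here: position 5 is the approach, 0 is open and 4 is the laparoscopic form; a final X marks a diagnostic procedure. On the same footing, CPT 47562 and 47563 are laparoscopic. The letter O in the third code may come from text extraction. It matters only if it is also in the query, where it would match nothing.

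**The plan's own figure.** 76/117 = 65.0% and 125/303 = 41.3%, a difference of 23.7 points, which agrees with the stated 24. Chi-square without correction is 19.0, p = 0.000013, consistent with p<0.001. The emergent-vs-elective odds ratio is (76 × 178)/(41 × 125) = 13,528/5,125 = 2.64.

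**Effect of a loss.** Let e be the emergent share and m the fraction of emergent operations missed, equal in both races, with no elective operation missed. The plan does not give m, so a range is shown. It equals the laparoscopic share of emergent operations times the share u of those with no listed CPT code in HPM. With an assumed 90% laparoscopic share, u = 25% gives m = 22.5% and u = 100% gives m = 90%.

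- Share of operations lost = e × m. The Black/White ratio of lost shares is 0.650/0.413 = 1.57, whatever m is.
- Ratio of captured shares = (1 − 0.650m)/(1 − 0.413m).
- Apparent emergent share = e(1 − m)/(1 − e × m).

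| m | Lost, Black | Lost, White | Captured ratio | Apparent emergent share, Black vs White |
|---|---|---|---|---|
| 0 | 0% | 0% | 1.00 | 65.0% vs 41.3% |
| 5% | 3.2% | 2.1% | 0.99 | 63.8% vs 40.0% |
| 10% | 6.5% | 4.1% | 0.98 | 62.5% vs 38.7% |
| 20% | 13.0% | 8.3% | 0.95 | 59.7% vs 36.0% |
| 22.5% | 14.6% | 9.3% | 0.94 | 59.0% vs 35.2% |
| 50% | 32.5% | 20.6% | 0.85 | 48.1% vs 26.0% |
| 90% | 58.5% | 37.1% | 0.66 | 15.6% vs 6.6% |

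The odds ratio is 2.64 in every row, because the factor (1 − m) multiplies the emergent odds in both races and cancels. Elective counts do not change in any row.

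**If the loss is not concentrated in emergent cases.** With 20% lost among both emergent and elective operations, the loss is 20% in each race. The captured ratio is 1.00 and the emergent shares stay at 65.0% and 41.3%.

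**Size on the cohort scale.** The percentages above are of operated patients. Scalability reports fewer than 1,000 treated against more than 9,400 untreated in six months: 1,000/10,400 = 9.6%, say 10% operated. This is an approximation, and the full study period may give a higher figure. With 10% operated in both races, the spurious Black-White gap is 0.10 × m × 23.7 points: about 0.5 points at m = 22.5% and 2.1 points at m = 90%. Among operated patients, a 5-point gap in capture, the size the plan says it can detect, needs m = 5/23.7 = 21%.

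**The case against.** The strongest reply is that the CPT codes already do the work. They are searched in the same source and include the two laparoscopic codes. If every inpatient operation in HPM carries one, nothing is lost. The plan's reference to codes as HPM lists them may even mean that the list reflects local recording. This stands as a possibility and sets the lower limit at nil. It does not settle the matter: the plan does not say that inpatient encounters carry CPT codes, and including PCS codes suggests that CPT alone was not thought sufficient.

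A second reply is that the documents define no code. That is correct, and the reading of the fifth and seventh characters must be confirmed. It is quickly checked.

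A third is that the bias is limited. This also stands. H1.1 concerns cholecystectomy in the elective setting. If only emergent cases are lost, the number of elective operations per diagnosed patient is untouched. The racial odds ratio for urgency is unchanged when loss is equal by race, and on the cohort scale the gap is about 2 points even at m = 90%, if about 10% are operated.

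A reader might infer that inpatient laparoscopic operations are in fact missed, that most are emergent, and that Black patients are therefore undercounted. The documents do not support that. They give neither the share of operations without a CPT code nor its distribution by urgency. Nor do they support a claim that the racial contrast in urgency is distorted; that would need loss that differs by race within urgency class.

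**Conclusion.** The code list is wrong as written, subject to confirming the code meanings: it has no laparoscopic PCS code and includes one code for a diagnostic excision. Severity is moderate. Whether operations are lost depends on an undocumented quantity, and the loss may be nil.

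If PCS-only recording falls mainly on emergent inpatient stays, the lost share is about 1.57 times larger in Black patients. The Black/White ratio of captured operations would then be 0.99 at 5% of emergent operations lost, 0.94 at 22.5% and 0.66 at 90%, with no true difference in operation rates. The exposed quantities are any-cholecystectomy, the absolute emergent shares and the cost strata. The emergent-vs-elective odds ratio and the elective count are not affected under equal loss by race. The figures also take the preliminary 65% and 41% as the true emergent shares; the plan does not say which codes produced them.

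**What to change.** Before the extraction is locked:

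- Add the laparoscopic PCS code(s), such as 0FT44ZZ, checked against the code tables.
- Remove 0FB40ZX.
- Confirm that the last code begins with zero in the query.
- State that either a CPT or a PCS match is enough.
- Cross-check captured operations against the operative log, by urgency and race, and report the proportion found by each code type.

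The cost is an edit to the code list and one query. The cross-check also supplies the missing quantity, the share of operations with no listed CPT code, and so shows whether the loss is real.

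### Aim 1 takes operative urgency from admission source alone, a route-of-arrival field with no stated mapping or check, although the elective/emergent split is the endpoint of H1.1 and H1.2

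*Combined protocol and SAP*

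**What the plan says.** The Aim 1 Clinical Outcomes paragraph identifies cholecystectomy by procedure codes and then states that "operative urgency (emergent/urgent vs elective) will be based on the admission source for the associated operative encounter". This is the only definition of urgency in the document.

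Two hypotheses depend on it. H1.1 is that "Black patients are less likely to undergo cholecystectomy in the elective setting than White patients". H1.2 is that "Time to consultation will modify the effect of race on elective cholecystectomy". Urgency is formally a secondary outcome; the Aim 1 primary outcome is cholecystectomy. The aims statement reads: "Secondary outcomes will include time from referral to consultation and treatment, completion of consultation, urgency of operative treatment, and cost".

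The rationale rests on the same split. Equity Plan and Impact reports emergent shares of "Black: 65% (76/117); White: 41% (125/303); p<0.001", and the Aim 1 power paragraph adds: "Note that preliminary data shows a difference of 24% in emergent chole". That paragraph also states: "We will be powered at 80% with an alpha of 0.05 to detect differences between Black and White patient outcomes as small as 5" percent.

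The Aim 1 chart review, described under Covariates, is confined to primary care notes. It collects dates of diagnosis, imaging, treatment discussion and surgical referral, plus prisoner status, and does not reach the operative encounter. The access-point variable (primary care or emergency department) is a separate item. Limitations does not mention misclassified urgency. Aim 2 lists emergent/urgent versus elective operation as a secondary outcome without defining it.

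**The concern.** Admission source is a proxy for urgency, and the plan leaves open how the proxy will be read. Two problems follow.

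- **The mapping is unstated.** If only emergency department arrivals count as emergent or urgent, a patient with acute disease who is admitted directly from a clinic, or transferred from another hospital, is scored elective. Leaving the mapping open also means it could be chosen after the data are seen.
- **No mapping fully solves it.** A planned admission and an urgent admission sent by the same clinic carry the same source. The field cannot tell them apart, whichever way that source is coded.

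At stake is the size of the racial difference in elective surgery, which is the subject of H1.1. H1.2 may be more exposed. A patient already under a surgeon could plausibly be admitted directly when acutely ill, while one without a surgeon comes through the emergency department. If so, classification error would track the modifier being tested. That is a possibility, not something the protocol documents. Adjusting for covariates does not remove error in the outcome itself.

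**Working it through.** **Inputs from the protocol.** Emergent operations: 76 of 117 Black patients and 125 of 303 White patients (Equity Plan and Impact). Stated gap 24 points; stated detectable difference 5 points (Aim 1 power paragraph).

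**Inputs assumed.** The protocol gives no accuracy for admission source. Sensitivity (Se) is the probability that a truly emergent or urgent operation is recorded as such, varied here from 0.8 to 0.95. Specificity is set to 1, so no elective operation is scored emergent. These values are illustrations only.

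**Step 1: reproduce the plan's figure.**
- Black: 76/117 = 64.96%. White: 125/303 = 41.25%.
- Difference: 64.96 − 41.25 = 23.7 points, which rounds to the stated 24.
- Pearson chi-square 19.00, p = 1.3 × 10⁻⁵, consistent with p<0.001.

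**Step 2: effect of misclassification.** With specificity 1, observed emergent share = true share × Se. Among operated patients the elective share is one minus this, so the elective gap has the same size and opposite sign. Take 64.96% and 41.25% as the true shares:

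| Se, Black | Se, White | Observed Black | Observed White | Observed gap (points) |
|---|---|---|---|---|
| 1.00 | 1.00 | 65.0% | 41.3% | 23.7 |
| 0.90 | 0.90 | 58.5% | 37.1% | 21.3 |
| 0.80 | 0.80 | 52.0% | 33.0% | 19.0 |
| 0.95 | 0.80 | 61.7% | 33.0% | 28.7 |
| 0.80 | 0.95 | 52.0% | 39.2% | 12.8 |

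Equal error shrinks the gap in proportion. Unequal error moves it in either direction.

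**Step 3: can error alone create a gap?** Let both groups have a true emergent share of 50%. Spurious gap = 0.50 × (Se in one group − Se in the other). For a sensitivity difference of 0.10 this is 0.50 × 0.10 = 0.05, or 5 points. This step does not use the preliminary data.

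**Step 4: could it explain the whole preliminary gap?** Only if the preliminary figures were themselves classified by source, which the protocol does not say. With Black sensitivity 1.0, White sensitivity would have to be 0.4125/0.6496 = 0.635, so that 41.25%/0.635 = 65.0%. That would be a large error in one group and none in the other.

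**The case against.** The strongest reply is that this is a gap in specification, not demonstrated misclassification. Much of that stands, and it rules out several stronger readings.

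- **That urgent direct admissions and transfers are scored elective.** A reader might infer this, but the protocol states no emergency-department-only rule. Transfers could be coded emergent or urgent. The claim holds only conditionally.
- **That the error differs by race.** A reader might set the catchment of "12 contiguous urban, suburban, and rural counties in the tri-state area of PA, NJ, and DE" against the three named emergency departments and conclude that arrival route follows race. Those departments are named as sites of cohort entry, not as the only routes to an operation. The protocol gives no transfer or direct-admission rates by county or race.
- **That the preliminary gap is inflated.** The protocol does not say how those operations were classified. If source was used with equal error in both groups, the true gap would be larger than 23.7 points, not smaller.
- **That the primary outcome is affected.** It is not. Cholecystectomy itself, completion of consultation and referral-to-consultation time do not use the urgency split.

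It is also fair to say that the protocol does not establish that Clarity holds an admission-type or case-class field, or that such a field is more accurate. Availability must be confirmed before relying on it.

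What the reply does not answer is that the rule, as written, uses a field that by its plain meaning records origin. Stating a mapping would help, but would not separate planned from urgent admissions with the same origin.

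**Conclusion.** The concern holds in a limited form. Operative urgency, a secondary outcome that nonetheless defines the endpoint of H1.1 and H1.2, rests solely on a route-of-arrival proxy with no mapping and no check. The size and direction of any bias cannot be determined from the protocol. On the assumptions above (sensitivities of 0.8 to 0.95, specificity 1), a true gap of 23.7 points could be observed as anything from 12.8 to 28.7. A between-group sensitivity difference of 0.10 at a 50% emergent rate is enough to produce the 5-point difference that Aim 1 says it can detect. None of this shows that the reported preliminary disparity is an artefact. The endpoint should be redefined before the data are analysed.

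**What to change.** Define urgency by the admission type/priority or operating-room case class recorded for the operative encounter, after confirming that Clarity holds one of them. Make the rule exhaustive: every unplanned admission, including direct admission and inter-hospital transfer, is emergent/urgent; every scheduled operation, whether same-day or with a planned stay, is elective.

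If neither field exists, pre-specify which admission-source values count as emergent/urgent, and check that mapping against a chart-reviewed sample within each racial group.

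In the first case, keep admission source as a sensitivity definition. Use the same urgency definition for the Aim 2 secondary outcome, which currently has none.

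The cost is one more data field and a revised paragraph, or a chart sample if no field is available. The preliminary 65% versus 41% may need to be re-run under the new definition to be comparable.
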